8.1. Immunogenicity assessments

Biological samples will be used for research planned in the protocol and for purposes related to the improvement, development and quality assurance of the laboratory tests described in this protocol.

Findings in this or future studies may make it desirable to use samples acquired in this study for research not planned in this protocol. In this case, all participants in countries where this is allowed will be asked to give consent to allow GSK or a contracted partner, to use the samples for further research. The further research will be subject to prior IEC/IRB approval, if required by local legislation.

Information on further research and its rationale can be obtained from GSK.

Sample testing will be done in accordance with the recorded consent of the individual participant/participant's parent(s)/LAR(s).

By default, collected samples will be stored for a maximum of 20 years. This storage period begins when the last participant performs the last study visit. This timeline can be adapted based on local laws, regulations or guidelines requiring different timeframes or procedures. In all cases, the storage period should be aligned with participant's consent. These additional requirements must be formally communicated to, discussed and agreed with GSK.

8.1.1. Biological samples (Amended 15 March 2022)

Table 10 Biological samples - Maternal participants (Amended 15 March 2022)

Maternal Sample type	Collected to evaluate	Minimum Quantity per participant	Unit	Time point	Additional information
Whole blood	Hematology, Biochemistry	~5.5	mL	Screening	Blood sample to be collected and analyzed locally only if not performed as per standard of care. ⁵
	Immune response ¹	~10	mL	Visit 1 (Day 1) pre-Dose	-
				Visit 2 (Day 31) ⁴	
Visit 3 (Delivery)					
Urine	Protein, Glucose	Dipstick	NA	Screening	Urine sample to be collected and analyzed locally only if not performed as per standard of care. ⁵
Nasal Swab ^{2, 3, 6}	Presence of RSV-A/B	-	-	MA-RTI Visit (Event-Driven)	Collect a nasal swab from any maternal participant who reports a MA-RTI.
				RTI hospitalization (Event-Driven)	Collect a nasal swab (if possible) from any participant hospitalized with RTI (or soon after discharge, as long as symptoms are ongoing).

¹ Volume of the blood sample collected for immune response assessment may be reduced to ~5 ml at investigator’s discretion. Refer to the laboratory manual for additional information.

² Collection of a nasal swab for sponsor testing is additional to and **DOES NOT REPLACE** any specimen collection (per local standard of care) for **testing by the local laboratory** to establish a fast and accurate diagnosis for the hospitalization. In the case of hospitalization, local testing for RSV infection should be performed if feasible.

³ If other nasal swab specimens are collected and tested locally as per local standard of care, results will be recorded in the eCRF. In principle only the sponsor laboratory results will be used when applying the case definitions for data analysis in Section 4.2.5.3. Thus, **where mandated by the protocol, every effort should be made to obtain nasal swab samples that can be analyzed by the sponsor (or sponsor-designated) laboratory.** Results of locally tested samples, with locally approved tests may be used when applying case definitions only in the event the nasal swab for central testing was impossible to collect.

⁴ Blood sample at Visit 2 (Day 31) will not be collected if the delivery occurs prior to Day 31 post-study intervention.

⁵ Blood sample for hematology, biochemistry evaluation should be tested and analyzed locally.

⁶ **Due to the change in the study requirements, nasal swab samples will no longer be collected from any maternal participant for RTI assessment.**

Table 11 Biological samples - Cord blood

Sample type	Collected to evaluate	Minimum Quantity per participant	Unit	Time point	Additional information
Cord blood	Immune Response	~5, up to ~10	ml	Visit 3 (Delivery)	-

Table 12 Biological samples – Infant participants (Amended 15 March 2022)

Infant Sample type	Collected to evaluate	Minimum Quantity per participant	Unit	Time point	Additional information
Whole Blood	Immune response - IF cord blood not collected	~2.5	mL	Visit 1-NB (Within 72 hours after birth)	Volume must be reduced if weight \leq 2.5 kg. [Trial-related blood loss for infant participants should be \leq 1 % at each timepoint. Total blood volume is estimated at 80 to 90 ml/kg body weight, and venipuncture should not exceed ~ 1.6 ml for a 2 kg baby or 2.0 ml for a 2.5 kg baby.] Refer to the Laboratory Manual for additional information. All minimum totals given below assume a body weight > 2.5 kg.
	Immune response – sub-cohort ⁴	~2.5 ¹	mL	Either Visit 2-NB (Day 43 post-birth) or Visit 3-NB (Day 121 post-birth) or Visit 4-NB (Day 181 post-birth)	
Nasal swab ^{2,3}	Presence of RSV-A/B	-	-	RTI Surveillance Visit - LRTIs (Event-Driven)	Collect at least one nasal swab for each potential LRTI reported. If more than one follow-up assessment visit is conducted, additional nasal swabs may be collected at the Investigator’s discretion.
				RTI Surveillance Visit - RTI hospitalization (Event-Driven)	Collect (if possible) from any participant hospitalized with a RTI (or soon after release, as long as symptoms are ongoing).

¹ Only from infant participants in the sample collection sub-cohort for the visit. Each infant is assigned to a single sub-cohort.

² Collection of a nasal swab for sponsor testing is additional to and **DOES NOT REPLACE** any specimen collection (per local standard of care) for **testing by the local laboratory** to establish a fast and accurate diagnosis for the hospitalization. In the case of hospitalization, local testing for RSV infection should be performed if feasible.

³ If other nasal swab specimens are collected and tested locally as per local standard of care, results will be recorded in the eCRF. In principle only the sponsor laboratory results will be used when applying the case definitions for data analysis in Section 4.2.5.3. Thus, where mandated by the protocol, every effort should be made to obtain nasal swab samples that can be analyzed by the sponsor (or sponsor-designated) laboratory. Results of locally tested samples, with locally approved tests may be used when applying case definitions only in the event the nasal swab for central testing was impossible to collect.

⁴ **Due to the change in the study requirements, there will no longer be collection of blood samples at Visit 2-NB, Visit 3-NB and Visit 4-NB.**

- An overall blood volume of approximately **30 mL** will be collected from maternal participants during the entire study period, if blood sample for assessing eligibility criteria should not be taken at screening.
- An overall blood volume of approximately **35.5 mL** will be collected from maternal participants during the entire study period, if blood sample for assessing eligibility criteria must be taken at screening.
- An overall blood volume of approximately **2.5 mL** will be collected from infant participants during the entire study period*. If cord blood sample cannot be collected, then an overall volume of **5 mL** will be collected*.

*** Due to the change in the study requirements, there will no longer be collection of blood samples from infant participants at Visit 2-NB, Visit 3-NB and Visit 4-NB.**

- Refer to [Table 10](#) and SoA (Setion 1.3) for details of volumes collected for different assessments.

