Distribute infant's participant card	0										Section 8.3.6
Distribute infant RTI diary card	0		0		0	0		0		0	Distribute at V1-NB: Distribute additional RTI diary cards as needed.
Review infant RTI diary card		0	0	0	0	0	0	0	0	0	
Collect infant RTI diary card			0		0	0		0		0	Collect RTI diary cards that are fully filled out.
Transcribe applicable infant RTI diary card data to eCRF		0	•	•	•	•	•	•	•	•	

CONFIDENTIAL

214725 (RSV MAT-012)
Protocol Amendment 1 Final

Visit / Contact	V1-NB	Safety contact (recommended) 5	V2-NB	C1-NB	V3-NB	V4-NB	C2-NB	V5-NB	RTI Surveillance		Notes
									Contacts (Section 8.4.2.2.1)	Visit	
Age of infant		8 days	6 weeks	3 months	4 months	6 months	9 months	12 months			
Visit Day	Birth	D8 Post-birth	D43 Post-birth	D91 Post-birth	D121 Post-birth	D181 Post-birth	D271 Post-birth	D366 Post-birth	Birth to Day 366 Post-birth	Event-Driven	
Demographic data	•										Section 5.3
Lifestyle characteristics ¹	•	0	•	•	•	•	•	•			
Apgar score (at 1, 5 and [if available/performed] 10 minutes)	•										
Weight, length, head circumference, physical examination	•		•		•	•		•		•	Section 8.2.2.1
Blood sample if no cord blood ~2.5 ml ²	•										Table 12
Blood sample (immunology, infants) ~2.5 ml ^{3,6}			• Sub-cohort 1		• Sub-cohort 2	• Sub-cohort 3					Table 12 Samples will no longer be collected at Visit 2-NB, Visit 3-NB and Visit 4-NB
Concomitant vaccinations	•	0	•	•	•	•					Sections 6.8.2 and 6.8.3
Concomitant medications	•	0	•	•	•	•	•	•	•	•	
Neonatal / Infant AESIs (Birth to 42 days post-birth)	•		•								Section 8.3.1, 8.3.3, 8.3.4, and 10.3.5. Must submit an Expedited AE report.
Suspected, probable and confirmed cases of COVID-19 infection	•	0	•	•	•	•	•	•	•	•	Sections 8.4.7

CONFIDENTIAL

214725 (RSV MAT-012)
Protocol Amendment 1 Final

Visit / Contact	V1-NB	Safety contact (recommended) 5	V2-NB	C1-NB	V3-NB	V4-NB	C2-NB	V5-NB	RTI Surveillance		Notes
									Contacts (Section 8.4.2.2.1)	Visit	
Age of infant		8 days	6 weeks	3 months	4 months	6 months	9 months	12 months			
Visit Day	Birth	D8 Post-birth	D43 Post-birth	D91 Post-birth	D121 Post-birth	D181 Post-birth	D271 Post-birth	D366 Post-birth	Birth to Day 366 Post-birth	Event-Driven	
(depending on the epidemiological COVID-19 situation) (Birth to 365 days post-birth)											
LRTIs (including medically assessed, RSV-associated LRTIs) (Birth to 365 days post-birth)	O ⁴	O ⁴	O ⁴	O ⁴	O ⁴	O ⁴	O ⁴	O ⁴	O ⁴	●	Sections 8.3.1, 8.3.3, 8.4 and 10.3.8.

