Medically assessed, RSV-associated hospitalizations (Birth to 365 days post-birth)	O ⁴	O ⁴	O ⁴	O ⁴	O ⁴	O ⁴	O ⁴	O ⁴	O ⁴	●	Sections 8.3.1, 8.3.3, 8.4 and 10.3.8.
SAEs, (S)AEs leading to study withdrawal, MAEs (Birth to 365 days post-birth)	●	O	●	●	●	●	●	●	●	●	Sections 7.2, 8.3.1 and 10.3.8
Symptom-directed physical examination (includes RTI signs, symptoms)										●	Section 8.4.4
Nasal swab										●	Sections 8.1.1 and 8.4.4.2
Study conclusion								●			Sections 4.4 and 10.1.9

LAR = legally acceptable representative; V= visit; C = contact; D=day; NB = newborn.

● indicates a study procedure that requires documentation in the individual eCRF.

○ indicates a study procedure that does not require documentation in the individual eCRF.

CONFIDENTIAL

214725 (RSV MAT-012)
Protocol Amendment 1 Final

¹ Record at Visit 1-NB and if changes in lifestyle characteristics thereafter.

² Adjust volume if weight \leq 2.5 Kg. If no cord blood was collected, an infant blood sample must be collected within 72 hours after birth.

³ One sample at one of these visits, as per infant's assigned sub-cohort. Adjust volume if weight \leq 2.5 Kg.

⁴ RTI unscheduled visit should be planned in case the infant participant has any symptoms or signs as defined in Section 8.4.3.2.

⁵ ***An additional recommended safety contact may be performed ~7 days post-birth if deemed necessary by the investigator or by the parent/ LAR(s).***

⁶ ***Due to the change in the study requirements, there will no longer be collection of blood samples at Visit 2-NB, Visit 3-NB and Visit 4-NB.***

In times of special circumstances, refer to Section 8 for study procedures.

Note:

Contact may be via telephone, SMS, email, video-telephone/telemedicine or other means, depending on local best practice. If the study site is the participant's primary healthcare facility, contact with study personnel may also be made in the context of a visit for routine or event-driven care.

The timing of an event-driven visit cannot be defined with precision in the protocol.

Table 3 Allowed windows for study visits (Amended 15 March 2022)

Visit	Study Day ^a	Allowed visit window ^b
Maternal participants		
Screening	Up to 28 days prior to Visit 1	Day (-28) - Day 1
Visit 1	Day 1	Day 1
Contact 1	Day 8	Day 8 – Day 12
Visit 2 ^c	Day 31	Day 21 – Day 46
Monthly contacts until delivery	every 30 days	every 25 – 35 days
Visit 3 (Delivery) ^d	-	1 day before to 3 days after delivery^e

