Visit 4	Day 43 after delivery	Day 31 - Day 61 after delivery
Contact 2	Day 181 after delivery	Day 166 - Day 201 after delivery
Infant participants		
Visit 1-NB (Birth) ^{d, e}	Birth	-
Recommended safety contact	Day 8	Day 7 - Day 10
Visit 2-NB	Day 43 after birth	Day 31 – Day 61 after birth
Contact 1-NB	Day 91 after birth	Day 84 - Day 98 after birth
Visit 3-NB ^f	Day 121 after birth	Day 111 – Day 141 after birth
Visit 4-NB ^f	Day 181 after birth	Day 166 – Day 201 after birth
Contact 2-NB	Day 271 after birth	Day 257 – Day 287 after birth
Visit 5-NB	Day 366 after birth	Day 331 – Day 401 after birth

^a Whenever possible the Investigator should arrange study visits at study days.

^b The investigator should endeavor to have the participants come in for the visits within this window.

^c Visit 2 (Day 31) may be replaced by Visit 3 (Delivery) in case of premature delivery. If the delivery date occurs prior to Day 31 post-study intervention, there will be no Visit 2 (Day 31).

^d If no cord blood was collected, an infant blood sample must be collected within 72 hours after birth.

^e If consent is not obtained within the allowed interval, but the parent(s) /LAR(s) still wish the infant to participate, consent may be obtained at any time until the Day 43 post-delivery/birth visit.

^f Visit may coincide with infant participant's routine care visit.

^g **For participants in whom a cesarean section is performed, the sample may be collected as soon as the participant arrives at the clinic and the intravenous line is inserted to prepare them for the cesarean section.**

Note: In times of special circumstances, refer to Section 8 for study procedures.

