8.1.3. Immunological read-outs (Amended 15 March 2022)

Table 14 Immunological read-outs (Amended 15 March 2022)

Blood sampling timepoint		Study group	Approximate No. participants	Component
Type of contact and timepoint	Sampling timepoint			
Maternal participants*				
Visit 1 (Day 1)	pre-study intervention	All study groups	378	RSV-A NAb RSV-B NAb RSV PreF3 Ab.IgG
Visit 2 (Day 31) ¹	post-study intervention	All study groups	378	RSV-A NAb RSV-B NAb RSV PreF3 Ab.IgG
Visit 3 (Delivery)	post-study intervention	Whole blood: All study groups Cord blood: All study groups	378	RSV-A NAb RSV-B NAb RSV PreF3 Ab.IgG
Infant participants*				
Visit 1-NB (Birth)	birth (only if cord blood cannot be collected)	Event-driven	Event-driven	RSV-A NAb RSV-B NAb RSV PreF3 Ab.IgG
Visit 2-NB (Day 43) ²	post-birth	RSV_MAT_BS1	84	RSV-A NAb RSV-B NAb RSV PreF3 Ab.IgG
		Control_BS1	42	RSV-A NAb RSV-B NAb RSV PreF3 Ab.IgG
Visit 3-NB (Day 121) ²	post-birth	RSV_MAT_BS2	84	RSV-A NAb RSV-B NAb RSV PreF3 Ab.IgG

Blood sampling timepoint		Study group	Approximate No. participants	Component
Type of contact and timepoint	Sampling timepoint			
		Control_BS2	42	RSV-A NAb RSV-B NAb RSV PreF3 Ab.IgG
Visit 4-NB (Day 181) ²	post-birth	RSV_MAT_BS3	84	RSV-A NAb
				RSV-B NAb
				RSV PreF3 Ab.IgG
		Control_BS3	42	RSV-A NAb RSV-B NAb RSV PreF3 Ab.IgG

RSV-A Nab = RSV-A neutralizing antibody; **RSV-B Nab** = RSV-B neutralizing antibody; **RSVPreF3 Ab.IgG** = RSV PreF3 antibody.immunoglobulin G.

¹ Blood sample at Visit 2 (Day 31) will not be collected if the delivery occurs prior to Day 31 post-study intervention.

² **Due to the change in the study requirements, there will no longer be collection of blood samples from infant participants at Visit 2-NB, Visit 3-NB and Visit 4-NB.**

* Refer to [Table 10](#), [Table 11](#), and [Table 12](#)

Table 15 Molecular biology tests (Amended 15 March 2022)

Nasal swab sampling timepoint		No. participants	Component ³
Type of contact (timepoint)	Sampling timepoint		
Maternal MA-RTI ^{1,4}	Event-driven	Event-driven	RSV-A RNA
			RSV-B RNA
Infant RTI ²	Event-driven	Event-driven	RSV-A RNA
			RSV-B RNA

¹ Includes maternal RTI hospitalizations

² Includes infant RTI hospitalizations

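### The 2.5 kg trigger for reducing the infant birth sample does not match Table 12's own 1% blood-loss limit; cap the draw at 0.8 mL/kg, maximum 2.5 mL

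*Protocol*

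**What the plan says.** Table 12 (Protocol Section 8.1.1) has a row labelled "Immune response - IF cord blood not collected". Its entry is about 2.5 mL, in the column for the minimum quantity per participant. The accompanying cell contains four statements:

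- **Trigger.** "Volume must be reduced if weight" is at or below 2.5 kg.
- **Limit.** "Trial-related blood loss for infant participants should be" at most 1% at each timepoint.
- **Basis and worked caps.** "Total blood volume is estimated at 80 to 90 ml/kg body weight, and venipuncture should not exceed" about 1.6 mL for a 2 kg baby or 2.0 mL for a 2.5 kg baby.
- **Scope.** The full volumes are said to assume a body weight above 2.5 kg, and the reader is sent to the Laboratory Manual for more.

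The infant Schedule of Activities (Section 1.3, Table 2) lists the same draw as "Blood sample if no cord blood ~2.5 ml". Its footnote 2 repeats the trigger ("Adjust volume if weight" is at or below 2.5 kg) but does not mention the 1% limit.

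Amendment 1 stopped the infant samples at Days 43, 121 and 181. The fallback birth sample remains: "If no cord blood was collected, an infant blood sample must be collected within 72 hours after birth".

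**The concern.** The cell gives sites two rules for one draw. The weight trigger tells them that above 2.5 kg the full 2.5 mL applies. The 1% limit, with the table's own blood-volume figures, allows 2.5 mL only for a heavier baby. The result is a step: a 2.5 kg newborn is capped at 2.0 mL, while one a few grams heavier comes under 2.5 mL.

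A site that follows the trigger would take more blood from a newborn than the protocol's own limit permits. The trial enrolls women with fetal growth restriction, pre-eclampsia, threatened preterm labor and twin pregnancies, so smaller babies are to be expected. What is at stake is compliance with a protective limit in newborns. No estimate or analysis set depends on it.

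**Working it through.** **Inputs**

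| Input | Value | Source |
|---|---|---|
| Birth sample without cord blood | about 2.5 mL | Table 12; Schedule of Activities, Table 2 |
| Weight at which volume must be reduced | 2.5 kg or less | Table 12; Table 2, footnote 2 |
| Blood-loss limit | 1% per timepoint | Table 12 |
| Blood volume | 80 to 90 mL/kg | Table 12 |
| Worked caps | about 1.6 mL at 2 kg; 2.0 mL at 2.5 kg | Table 12 |

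**Step 1: reproduce the plan's caps.** Maximum draw = 0.01 × blood volume per kg × weight.

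- At 80 mL/kg: 0.01 × 80 × 2.0 = 1.6 mL and 0.01 × 80 × 2.5 = 2.0 mL. Both stated caps are matched exactly.
- At 90 mL/kg: 1.8 mL and 2.25 mL. Neither is matched.

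The table therefore works at the cautious end of its range, 0.8 mL/kg.

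**Step 2: the weight at which 2.5 mL is exactly 1%.** Weight = 2.5 / (0.01 × blood volume per kg).

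- 80 mL/kg: 2.5 / 0.80 = 3.125 kg
- 85 mL/kg: 2.5 / 0.85 = 2.94 kg
- 90 mL/kg: 2.5 / 0.90 = 2.78 kg

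For this weight to be 2.5 kg, blood volume would have to be 2.5 / (0.01 × 2.5) = 100 mL/kg, outside the stated range.

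**Step 3: size of the excess.** Share drawn = 2.5 / (blood volume per kg × weight). Excess = 2.5 mL minus the 1% cap.

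| Weight | 1% cap, 80 mL/kg | Share | Excess | 1% cap, 90 mL/kg | Share | Excess |
|---|---|---|---|---|---|---|
| just above 2.5 kg | 2.00 mL | 1.25% | 0.50 mL | 2.25 mL | 1.11% | 0.25 mL |
| 2.6 kg | 2.08 mL | 1.20% | 0.42 mL | 2.34 mL | 1.07% | 0.16 mL |
| 2.8 kg | 2.24 mL | 1.12% | 0.26 mL | 2.52 mL | 0.99% | none |
| 3.0 kg | 2.40 mL | 1.04% | 0.10 mL | 2.70 mL | 0.93% | none |
| 3.125 kg | 2.50 mL | 1.00% | none | 2.81 mL | 0.89% | none |

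**Step 4: the proposed rule.** Volume = the smaller of 0.8 mL/kg × weight and 2.5 mL. This gives 1.60 mL at 2.0 kg, 2.00 mL at 2.5 kg, 2.08 mL at 2.6 kg, 2.24 mL at 2.8 kg, 2.40 mL at 3.0 kg, and 2.50 mL from 3.125 kg. Up to 3.125 kg the draw is 1.00% of blood volume at 80 mL/kg and 0.89% at 90 mL/kg; above that weight the share is lower. Both existing caps are kept and the step at 2.5 kg disappears.

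**The case against.** The strongest reply is that the 1% sentence covers all infants, with no weight restriction. The trigger says when a reduction is mandatory; it does not forbid one at higher weights. Read together, the 1% ceiling always governs, and a site that applies it would already draw less. On this reading the text is unclear but does not direct an overdraw. The reading is possible. Against it, the reduction is worded as mandatory and the limit only as advisory, the full volumes are tied to weights above 2.5 kg, and footnote 2 of the schedule gives the trigger alone. Table 10 lets investigators reduce the mothers' immune-response sample at their discretion; Table 12 has no similar allowance for infants above 2.5 kg.

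The Laboratory Manual may contain weight bands. It is not available here, so an actual overdraw cannot be shown. Bands that respected the 1% limit would still conflict with the protocol's trigger.

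The inputs are approximate: the volume is about 2.5 mL, blood volume is an estimated range, and at 90 mL/kg the excess is at most 0.25 mL. That limits the size, but the mismatch remains across the whole range. It is also fair that 0.9 mL/kg could be defended from the stated range. The choice of 0.8 rests on the two worked caps, which only 80 mL/kg reproduces.

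Finally, few infants are affected and the period was short. Willingness to provide cord blood was an inclusion criterion, and the draw is scheduled at "birth (only if cord blood cannot be collected"). Vaccination stopped on 25 February 2022. A woman dosed at 24 weeks on that day would reach 40 weeks (an assumed delivery time) 112 days later, on 17 June 2022, about three months after the amendment of 15 March 2022. This stands, and it keeps the consequence small.

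**Conclusion.** The concern holds. No blood volume between 80 and 90 mL/kg reconciles the 2.5 kg trigger with the 1% limit. On the table's own 0.8 mL/kg basis, the full sample exceeds the limit in infants above 2.5 kg and below 3.125 kg; on the most lenient basis, above 2.5 kg and below about 2.78 kg. The excess is greatest just above 2.5 kg and falls to zero at the upper end of each band.

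This assumes that a site acts on the trigger and draws the nominal 2.5 mL. The documents do not say how many infants without cord blood fall in the band, or what the Laboratory Manual instructs. It is a small but real inconsistency in a safeguard for newborns and should be corrected. It has no bearing on the statistical results.

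**What to change.** In Table 12 and in footnote 2 of the infant Schedule of Activities, replace the 2.5 kg trigger with: *Draw at most 0.8 mL per kg body weight, up to a maximum of 2.5 mL (that is, reduce the volume below about 3.1 kg).* Table 12's remark that the full volumes assume a weight above 2.5 kg should be brought into line. Check that the Laboratory Manual says the same.

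The cost is one sentence, one footnote and the manual check. Infants in the affected band would give at most 20% less blood (0.5 / 2.5, just above 2.5 kg), and 4% less at 3.0 kg (0.10 / 2.5). Slightly less serum would then be available for the three antibody assays. The protocol already accepts reduced volumes from babies at or below 2.5 kg, so smaller samples are already foreseen.

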4.2.5.3. RSV infection (Amended 15 March 2022)

The sponsor will analyse nasal swabs by quantitative reverse transcription polymerase chain reaction (qRT-PCR) for the presence of RSV-A/B. A positive (RSV-A or B) test result constitutes a case of RSV infection. Refer to [Table 10](#), [Table 12](#) and [Section 8.4](#).

In the event the collection of a nasal swab for testing by the sponsor is impossible, results from locally collected samples, tested with locally approved tests, may also be considered for the determination of a case of RSV infection.

Note: Due to the change in the study requirements, RTI surveillance of the maternal participants will no longer be performed.

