8.4.3.2. For an infant RTI (Amended 15 March 2022)

Conduct an assessment visit, as described in Section 8.4.4, as soon as possible after at least one of the following has been reported during the surveillance period:

- Difficulty in breathing.
- Wheezing.
- The maternal participant/LAR intends to seek medical care because of concern about the infant's RTI, or general health in the context of the infant's RTI.

[figure not shown]
The visit should take place as soon as possible; ideally within 72 hours. However, a visit may be conducted even beyond the specified ideal window if symptoms are ongoing.

- After the first assessment visit, site personnel should use results of additional contacts to assess the development of new and worsening of previously reported symptoms.
- Site personnel should conduct a **follow-up** assessment **visit** as soon as possible after learning:
 - that any symptom present at the first assessment visit has worsened, OR
 - that there are new symptoms of difficulty in breathing or wheezing, OR
 - that there is new or increased parental concern in the context of the RTI.

The timing of the follow-up visit should be consistent with the guidance given above.

A decision tree is provided in [Figure 5](#). Refer to the SPM for additional details regarding infant RTI surveillance.

Figure 5 Decision Tree for site personnel - infant surveillance and assessment (Amended 15 March 2022)

RR: Respiratory rate; SpO₂: Blood oxygen saturation by pulse oximetry.

¹Details regarding Surveillance are provided in Section 8.4.2.2 and the SPM.

²Cough, runny nose, blocked nose, difficulty in breathing, wheezing are described in Section 8.4.1.2

³Details regarding the RTI assessment visit are provided in Section 8.4.4 and the SPM.

⁴Post-visit follow-up is described in Sections 8.4.6 and in the SPM.

⁵If a follow-up assessment visit is conducted, collection of additional nasal swabs is as described in Table 12.

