9.3.1.1.3. Maternal and Infant participants

- Diagnosis during the study with an immunological disorder or occurrence during the study of a condition (other than the study pregnancy) capable of altering immune response. For evaluation of immunogenicity endpoints in maternal and infant participants, this includes RSV infection confirmed either locally or by GSK during the specified analysis interval.
- Any investigational or non-registered product (drug or vaccine) other than the study vaccine/product administered during the specified analysis interval.

9.3.1.2. Other situations that may lead to elimination of a participant (maternal / infant) from per protocol analyses (immunogenicity)

- Protocol violation(s) linked to the inclusion/ exclusion criteria, including maternal age at Visit 1 (study intervention).
- Study intervention not administered as specified by the protocol.
- Failure to comply with the post-dose immunogenicity blood sampling schedule at a given time point (Table 3).

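### Local RSV results count only if the central swab could not be collected, so a locally positive infant whose collected swab yields no valid result is left unconfirmed

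*Protocol*

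**What the plan says.** Protocol Table 7 and SAP Table 10 make confirmed RSV infection a component of RSV-LRTI, severe RSV-LRTI and RSV hospitalisation. Protocol 4.2.5.3 defines confirmation as a positive sponsor qRT-PCR and then gives one exception: "In the event the collection of a nasal swab for testing by the sponsor is impossible, results from locally collected samples", if tested with locally approved tests, may also be taken into account. SAP 4.1.2.3 repeats this.

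In Protocol 8.1.1, footnote 3 to Table 12 (infants) and footnote 3 to Table 10 (mothers) set the default: "In principle only the sponsor laboratory results will be used when applying the case definitions for data analysis in Section 4.2.5.3". They then limit the exception: local results "may be used when applying case definitions only in the event the nasal swab for central testing was impossible to collect".

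The local information is meant to exist. For admitted participants, "In the case of hospitalization, local testing for RSV infection should be performed if feasible". The footnotes also state: "If other nasal swab specimens are collected and tested locally as per local standard of care, results will be recorded in the eCRF".

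The infant endpoints are secondary, counted from birth to 365 days and tabulated as number and percentage by group (Protocol 9.4.4.1, SAP 4.3.1.1). SAP section 2 says that no hypotheses are tested.

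**The concern.** Collecting a swab and obtaining a result are separate steps. Between them a sample can be lost, arrive in poor condition, be too small, or fail in the assay. Once the swab has been taken, the stated exception no longer applies, whatever happens to it afterwards. The positive local test then sits in the eCRF without being eligible for the case definition.

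Failure after collection is foreseeable. Amendment 1 dropped central hematocrit because samples in several countries did not reach the laboratory in time. Hematocrit blood is not a swab and its stability may differ, but this is evidence of transport failure within this trial. Protocol section 8 also allows families to take the infant's swab themselves in special circumstances.

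The second problem is the permissive wording. Even where the exception applies, the local result only *may* be used, and the study has been fully unblinded (Protocol 6.3.5). Whether a given local positive enters the count is therefore open to a decision made with treatment known.

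**Working it through.** The plan gives no RSV rate, no invalid-swab rate and no count of affected infants, so there is no figure to reproduce. The check is a reading of the rule, followed by an illustration on stated assumptions.

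**Step 1: the rule applied to an infant who meets the clinical criteria.**

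| Central swab | Local test | As written | With the fix |
|---|---|---|---|
| Valid, positive | any | confirmed | confirmed |
| Valid, negative | positive | not confirmed | not confirmed; seen in a sensitivity count |
| Impossible to collect | positive | may be confirmed | confirmed |
| Collected; lost, insufficient or invalid | positive | not confirmed | confirmed |
| No valid result | none or negative | not confirmed | not confirmed |

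The fourth row is the fault. The third row is the discretion. SAP 6.2.3.2 says that absent laboratory results are not substituted, so it supplies no fallback.

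**Step 2: what a loss would do.** Let f be the share of true cases in the fourth row. Perfect specificity is assumed, and f and the RSV rates are assumptions. Group sizes are the planned 252 and 126; enrolment stopped early, so the actual numbers will be lower.

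Counted rate = true rate × (1 − f).

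- True rates 2% (vaccine) and 4% (control): 252 × 0.02 + 126 × 0.04 = 5.04 + 5.04 = 10.08 cases. With f = 5%, 10%, 20%, the loss is 0.5, 1.0, 2.0 cases.
- True rates 5% and 10%: 12.6 + 12.6 = 25.2 cases. The loss is 1.3, 2.5, 5.0 cases.
- With f = 0, nothing is lost.

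**Step 3: effect on the group contrast.** If f is equal in both groups, it cancels from the risk ratio, which stays at 0.50. The risk difference shrinks by (1 − f): at 5% against 10% and f = 10%, from 5.0 to 5.0 × 0.9 = 4.5 points. If f differs, the ratio moves:

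- 20% lost in control only: 0.50 × 1 / 0.80 = 0.625.
- 20% lost in vaccine only: 0.50 × 0.80 / 1 = 0.40.

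These unequal cases are extremes chosen to show direction. Nothing in the documents says that the loss is unequal, but with the study unblinded, equality cannot be taken for granted.

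**The case against.** The strongest reply is that the documents never say such an infant is a non-case. The default is qualified as a matter of principle, sites are asked for swabs that can be analysed, and invalid results are simply not mentioned. This is fair as to intent. But the sentence that admits local results carries the word *only* and names one situation, and an invalid result is not that situation.

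Other points stand and limit the concern. Central qRT-PCR is the programme's stated core assay (Protocol 8.1.2), and preferring one assay to varied local ones is defensible. Repeat swabs are allowed at follow-up visits. Respiratory admissions are still reported as SAEs, so what is lost is the RSV label and not the safety event. SAP 4.3.1.2.5 allows an exploratory RSV-LRTI definition, but only if judged necessary, which does not settle the rule in advance. Changing a definition after unblinding also needs care.

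Two stronger readings are tempting and are not supported:

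- *A late negative central swab wrongly overrides an earlier local positive.* Late swabs are allowed: "However, a visit may be conducted even beyond the specified ideal window if symptoms are ongoing", and for admitted infants "or soon after release, as long as symptoms are ongoing". But a late positive counts, and both allowances require continuing symptoms. If symptoms resolve first, the visit is missed and the local result is arguably admissible. Overruling a valid central negative would trade away central primacy. The 72 hours in Protocol 8.4.3.2 is an ideal target for the visit, not a limit between two samples.
- *The protocol contradicts itself because per-protocol elimination accepts either source.* In Protocol 9.3.1.1.3, "this includes RSV infection confirmed either locally or by GSK during the specified analysis interval". That is a wide net for removing possible confounding from immunogenicity, which is a different purpose. Infant blood sampling after birth has also been stopped, so the overlap is small.

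**Conclusion.** The point holds for the collected-but-no-valid-result case and for the permissive wording. It is a misplaced condition in a stated rule, and it can turn a true RSV-LRTI or RSV hospitalisation into an unconfirmed episode.

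Its size is unknown. A reader might infer a particular percentage undercount, but any such figure only restates the share of cases assumed lost. If RSV counts are in single digits, one or two reclassified infants would be visible in the table. If no swab fails after collection, nothing changes. No primary endpoint or hypothesis test depends on it. It is worth correcting because the repair is cheap and removes a choice that would otherwise be made after unblinding.

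**What to change.** In Protocol 4.2.5.3, footnote 3 of Tables 10 and 12, and SAP 4.1.2.3:

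1. Change the trigger to: no valid central qRT-PCR result is available for the episode (swab not collected, lost, insufficient or invalid).
2. State that a locally approved test result from the same episode *will* be used in that situation, in place of the two permissive phrases. SAP 4.1.2.4 already separates episodes by at least 7 symptom-free days.
3. Keep a valid central result decisive in the main analysis, with no time-based override.
4. Report two sensitivity counts beside the main one: central-only, and any local or central positive. The second shows the discordant pairs.

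The cost is wording and two extra rows, with no new sampling. Local results are to be recorded in the eCRF; the sponsor should confirm that local sample dates are also held, since matching to an episode needs them. The downside is that local assays vary between sites and the definition changes after unblinding. The central-only count covers both, and the reason for the change should be recorded in SAP 4.8.
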